5. OBJECTIVES AND PURPOSE

Due to its travel-friendly size and eco-friendliness, toothpaste tablets have gained popularity among the green people. Green people are those who aim to achieve sustainability. Despite toothpaste tablets' many merits, there is only scarce information on the efficacy, consumer satisfaction, cost, and benefits. Therefore, the purpose of our study is to evaluate the efficacy of toothpaste tablets when compared to conventional toothpaste in removing plaque. We aim to evaluate this by, measuring gingival index (GI) and the plaque index (PI) on subjects that have been either using the tabs or toothpaste.

We hypothesize that there will be no statistically significant difference in GI and PI scores between the two groups. The results of the study will be highly significant as it will serve as a strong piece of evidence to recommend or not to recommend this newly developed product that has the potential to keep our planet safe from non-degradable plastic.

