GI Index Interpretation,

0.1–1.0: Mild gingivitis

1.1–2.0: Moderate gingivitis

2.1–3.0: Severe gingivitis

For measuring plaque accumulation, the Turesky Modified version contains a basis from 0-5, while also distinguishing severity and location. The same six teeth will be used.

The PI scores will indicate as follows,

0: No plaque.

[figure not shown]
1: Separate flecks of plaque at the cervical margin of the tooth.

2: A thin continuous band of plaque at the cervical margin of the tooth.

3: A band of plaque wider than 1 mm covering less than 1/3rd of the crown of the tooth.

4: Plaque covering at least $1/3^{rd}$ but less than $2/3^{rd}$ of the crown of the tooth.

5: Plaque covering $2/3^{rd}$ or more of the crown of the tooth.

Given the environmental advantages of toothpaste tabs, it is worth exploring the effectiveness of tabs following the action of daily brushing within a 2-week trial period.

After measurements are recorded, comparison of the GI & PI results between tabs and conventional toothpaste will be assessed.

a. Endpoints

Primary endpoints

GI and PI scores between the use of dental tablets and conventional toothpaste.

Secondary endpoints

Satisfaction on user-friendliness of both types of toothpastes.

b. Overall study design

A convenience sample of 40 participants will be randomized into two groups containing 20 individuals each. Randomization will be performed by using a randomization table that is generated by the statistician. Selection of participants will concur to a written consent primarily based on voluntary agreement restricted only to a student consensus.

Group A. Colgate Cavity Protection will be selected as the conventional toothpaste for the control group due to its low abrasivity⁸.

Group B. Colgate Anywhere Toothpaste Tablets will be used as the prime cleansing agent for the experimental group.

Subjects will be instructed to use their normal oral hygiene routine throughout a 2-week timeline. New toothbrushes will be used for both groups—Colgate Slim Soft Gliding Tips Toothbrush, Extra Soft, Compact Head.

Group B will be instructed to use Colgate Anywhere toothpaste tablets where one tablet will be used for brushing. Subjects will gently chew on the tablet to dissolve it and will brush for two minutes at least twice a day. Any residual excess from the tablets are to be spit out. Group A will use Colgate Cavity Protection toothpaste and brush at least twice a day for two minutes.

c. Study Procedures and Schedule

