13. SUBJECT WITHDRAWAL OR TERMINATON

Reasons for withdrawal or termination: Subjects will have the freedom to withdraw at any time point of the study.

Handling of subject withdrawals or termination: Records will be kept on subjects that choose to withdraw and the reason why.

Premature termination or suspension of study: N/A

14. **COMPENSATION**

No compensation will be given to participants

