17. STATISTICAL ANALYSIS

We hypothesize that there will be no statistically significant difference in GI and PI scores between the two groups. To test this hypothesis, we will use an independent sample t-test to compare the difference in GI and PI scores between the two groups. If it is determined that GI and/or PI are not normally distributed, we will proceed with testing our hypothesis with the Mann-Whitney U-test. This hypothesis will be tested at an alpha level of 0.05 and will be two-sided. A sample size analysis was conducted and demonstrated that 20 samples per group were necessary to achieve 80% power to test this hypothesis at an alpha level of 0.05.

18. DATA AND SAFETY MONITORING PLAN (DSMP)

N/A

19. LITERATURE REFERENCES

- 1. Gängler, Peter et al. "In vitro effect of fluoride oral hygiene tablets on artificial caries lesion formation and remineralization in human enamel." *BMC oral health* vol. 9 25. 2 Oct. 2009, doi:10.1186/1472-6831-9-25
- 2. Shaikh, Mohammed et al. "Micro computed tomography analysis of abrasivity of toothpaste tablets compared to conventional toothpaste." *American journal of dentistry* vol. 34,5 (2021): 235-239.
- 4. Chasma, Farida, and Gary Cousin. "Keeping Teeth Clean but Not at the Environment's Expense." *Faculty Dental Journal*, vol. 12, no. 1, 2021, pp. 20–22., https://doi.org/10.1308/rcsfdj.2021.5. https://www.researchgate.net/publication/348155830 Keeping teeth clean but not at the environment's expense
- 5. Moslehzadeh, Kaban. "Quigely Hein Index (modified). *Malmo University*. 27 Apr. 2016, https://www.mah.se/CAPP/Methods-and-Indices/Oral-Hygiene-Indices/Quigely-Hein-Index-modified/
- 6. Lippert F. An introduction to toothpaste its purpose, history and ingredients. *Monogr Oral Sci* 2013; 23:1-14.
- 7. 300 million toothpaste tubes go to landfill. *Br Dent J* 2021; 230-390.

- 8. Löe H. The Gingival Index, the Plaque Index and the Retention Index Systems. J Periodontol. 1967 Nov-Dec;38(6):Suppl:610-6. doi: 10.1902/jop.1967.38.6.610. PMID: 5237684.
- https://aap.onlinelibrary.wiley.com/doi/abs/10.1902/jop.1967.38.6.610?sid=nlm%3Apubmed

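### The 80% power claim has no effect size, SD, margin or index behind it; at 20 per group it corresponds to about 0.91 SD, so a non-significant result would not support 'no difference'

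*Combined protocol and SAP*

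**What the plan says.** Sections 5 and 17 state the hypothesis in the same terms: "We hypothesize that there will be no statistically significant difference in GI and PI scores between the two groups". Section 17 names the test, "we will use an independent sample t-test to compare the difference in GI and PI scores between the two groups", with a Mann-Whitney U-test if the scores are not normally distributed, and adds: "This hypothesis will be tested at an alpha level of 0.05 and will be two-sided". The sample size rests on one sentence, which claims that "20 samples per group were necessary to achieve 80% power to test this hypothesis at an alpha level of 0.05". Section 6 fixes the allocation: "A convenience sample of 40 participants will be randomized into two groups containing 20 individuals each".

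Section 17 does not give the difference assumed, the SD, an equivalence or non-inferiority margin, or which of the two indices the calculation concerned.

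On use of the result, Section 5 says that it "will serve as a strong piece of evidence to recommend or not to recommend this newly developed product". Section 12 (Potential Benefits) counts as a benefit the showing that tablets and toothpaste do not differ clinically or statistically, and expects that this may lead the public to switch.

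**The concern.** The plan runs a test designed to detect a difference, hopes that it will be non-significant, and intends to report that outcome as evidence that the products perform alike. The power sentence makes this look safe, because a reader will take a null result as coming from a trial adequately sized for its hypothesis.

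Power of a difference test always belongs to a particular difference. Without that difference, 80% cannot be checked, and a reader cannot tell which differences the trial would probably miss. If the detectable difference is large compared with what a dentifrice might change in two weeks, non-significance says little about whether the tablets are as good as the paste. At stake is a product recommendation drawn from a null result.

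**Working it through.** **Inputs from the plan.** n = 20 per group (Sections 6 and 17); alpha = 0.05, two-sided; independent t-test; stated power 80% (Section 17). Effect size, SD and margin: not given.

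**Step 1. Can the plan's figure be reproduced?** No, because the assumed difference is missing. The calculation can only be solved backwards for the difference that gives 80% power.

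**Step 2. Detectable difference in SD units.**
- Normal approximation: d = (z0.975 + z0.80) × √(2/n) = (1.960 + 0.842) × √(2/20) = 2.802 × 0.3162 = 0.886.
- Exact, noncentral t with 38 df: d = 0.909.
- Exact power at other values: 33.8% at d = 0.5; 69.3% at d = 0.8 (80% would need 26 per group); 79.2% at d = 0.9.
- With the Mann-Whitney fallback (relative efficiency 0.955), d = 0.93.

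This step uses only the plan's own inputs.

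**Step 3. Conversion to index points, for scale only.** The SDs come from the appended results tables, not from planning assumptions. Pooled SD = √((s1² + s2²)/2). Change SDs are recovered from the Table 4 intervals as half-width ÷ 2.093 × √20, then pooled.

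| SD source | PI SD | 0.909 × SD | GI SD | 0.909 × SD |
|---|---|---|---|---|
| Two-week, Table 3 (PI 0.49, 0.48; GI 0.26, 0.18) | 0.485 | 0.44 | 0.224 | 0.20 |
| Baseline, Table 2 (PI 0.58, 0.46; GI 0.26, 0.24) | 0.523 | 0.48 | 0.250 | 0.23 |
| Change, from Table 4 (PI 0.489, 0.370; GI 0.193, 0.126) | 0.434 | 0.39 | 0.163 | 0.15 |

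**Step 4. Comparison with the observed change.** Table 4 gives two-week PI reductions of 0.224 (tablet) and 0.218 (conventional). With the two-week SD the ratio is 0.441/0.224 = 1.97 to 0.441/0.218 = 2.02; across the three SDs it runs from about 1.8 to 2.2. For a between-group PI difference of 0.218, d = 0.218/0.485 = 0.449 and exact power is 28%. It is 25% with the baseline SD and 34% with the change SD. The GI reductions are 0.026 and 0.011, far below the 0.15 to 0.23 points detectable.

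**Step 5. What the reported interval excludes.** Table 3 gives a between-group 95% interval for two-week PI of -0.25 to 0.417. Both limits exceed 0.224 in size, so a difference as large as either arm's whole reduction is not excluded in either direction.

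**Step 6. Reliability of the tables.** They are not fully consistent.
- In Table 3 the PI means differ by 2.59 - 2.56 = 0.03, but the stated mean difference is 0.08.
- In Table 4 the tablet PI row has p = 0.017 beside an interval that crosses zero (-0.453 to 0.005); a paired t-test from that interval gives p of about 0.055.
- In Table 4 the conventional PI interval implies p of about 0.016, against a stated 0.035.

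Step 5 does not depend on which PI difference is right. Centring on 0.03 with SE = 0.485 × √(2/20) = 0.153 and t = 2.024 gives 0.03 ± 0.31, or -0.28 to 0.34, which leads to the same conclusion.

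**The case against.** The strongest reply is that nothing has been shown to be wrong. If the unreported assumption was a difference of about 0.9 SD, then 20 per group and 80% agree. Power to test a hypothesis is also common shorthand for the power of a test of that null. This stands: a reader might infer that the 80% is false, but the documents support only that it cannot be verified.

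A reader might also infer that no calculation aimed at showing no difference could give 20 per group. That is not so. Two one-sided tests at 0.05 with a true difference of zero reach 80% at 20 per group for a margin of about 0.94 SD. A non-inferiority calculation (one-sided 0.025) does so for about 0.43 PI points, using the two-week SD. The documents neither report such a calculation nor rule one out, so it cannot be asserted that the sample size was not derived to show absence of a difference.

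The point-scale figures deserve the objection that they use observed results in place of planning inputs, and that the tables conflict in places. Nor does the plan make the before-after change the relevant between-group difference: both arms also received new toothbrushes, so that change is not purely a dentifrice effect. These figures are illustrations of scale; the 0.91 SD does not depend on them.

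It is also fair that Section 5 does not tie its claim of strong evidence to the power figure, and that Table 3 already prints intervals. But printing intervals does not help if the conclusion is drawn from the p-value, which is what the hypothesis as worded invites.

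**Conclusion.** The point holds as a claim that cannot be verified, joined to an inference that the design does not support. On the plan's own inputs, 80% power at 20 per group corresponds to about 0.91 SD on a single index. This assumes 20 evaluable participants per group, an independent t-test, two-sided alpha 0.05 and no multiplicity adjustment. Nothing in the plan argues that smaller differences are unimportant, and there is no margin, so a non-significant result cannot be read as no difference.

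The 0.91 SD is firm. The conversions (about 0.44 PI points or 0.20 GI points, and about 28% power for a PI difference of about 0.22) rest on observed SDs and should be read with the ranges shown. The documents do not support going further and calling the 80% an arithmetical error.

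**What to change.** 1. **Section 17.** Replace the power sentence with wording such as: *20 per group gives 80% power to detect a between-group difference of about 0.91 SD on a single index (two-sided alpha 0.05, t-test); this is not power to show absence of a difference.* If the original effect size, SD and index exist, state them there. Label any conversion to PI or GI points as based on observed SDs, so that it is not taken for a planning assumption.
2. **Sections 5, 12 and 17.** Remove the step from non-significance to no difference, and the description of the result as strong evidence. Limit the conclusion to the differences that the between-group 95% confidence interval excludes, separately for GI and PI. Check the table entries listed in Step 6 before quoting the intervals in support.

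The cost is wording only, with no extra participants or visits. The downside for the sponsor is that the stated claim becomes less favourable. A margin chosen now, with results already appended, would be post hoc and is not proposed.

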- 9. "Amazon.com: Colgate Anywhere Travel Toothpaste Tablets with Fluoride ..." *Amazon*, https://www.amazon.com/Colgate-Anywhere-Toothpaste-Anti-Cavity-Refillable/dp/B08KQMC5MJ.
- 10. "Cavity Protection Toothpaste: Colgate®." *Cavity Protection Toothpaste* | *Colgate*®, https://www.colgate.com/en-us/products/toothpaste/cc-cavity-protection.
- 11. Moslehzadeh, Kaban. "Quigely Hein Index (modified). *Malmo University*. 27 Apr. 2016, https://www.mah.se/CAPP/Methods-and-Indices/Oral-Hygiene-Indices/Quigely-Hein-Index-modified/
- 12. Wilkins, Esther M., et al. *Clinical Practice of the Dental Hygienist*. 12th ed., Wolters Kluwer, 2017, pp. 372, 400.
- 13. *Amazon.com : Colgate Slim Soft Gliding Tips Toothbrush, extra soft ...* (n.d.). Retrieved August 30, 2022, from https://www.amazon.com/Colgate-Gliding-Toothbrush-Extra-Compact/dp/B07NXDWX78

Schedule of Events

	VISIT 1 (Day/Week/Month)	VISIT 2 (Day/Week/Month)
Informed Consent	X	
Baseline Oral Examination (GI & PI)	X	
Distribution of Product	X	
Post 2-Week Oral Examination (GI & PI)		X
Survey Distribution		X
Weight		
Vital Signs		
Oximetry		
Spirometry		

RESULTS

Table 1. Summary of Gender and Age for Subjects Who Completed the Two-Week Clinical Study

	Nun	Age			
Dentifrice	Male	Female	Total	Mean	Range
Sodium Fluoride Toothpaste1	8	12	20	25	18-36
Sodium Fluoride Toothpaste Tablet2	6	14	20	25	19-30

Table 2. Summary of the Baseline Loe-Silness Gingival Index Scores and Quigley-Hein Plaque Index Scores

	Dentifrice	N	Baseline (Mean±SD)		p-value	95% Confidence Interval	
Parameter				Mean Difference		Lower	Upper
Gingivitis	Toothpaste Tablet	20	1.35±0.26	-0.08	0.47	-0.19	0.13
	Conventional Dentifrice	20	1.37±0.24				
Plaque	Toothpaste Tablet	20	2.80±0.58	0.06	0.665	-0.36	0.38
	Conventional Dentifrice	20	2.78±0.46				

Table 3. Summary of the two-week Loe-Silness Gingival Index Scores and Quigley-Hein Plaque Index Scores

Parameter	Dentifrice	N	Two-Week (Mean±SD)		p-value	95% Confidence Interval	
				Mean Difference		Lower	Upper
Gingivitis	Toothpaste Tablet	20	1.33±0.26	-0.06	0.37	-0.167	0.083
	Conventional Dentifrice	20	1.34±0.18				
Plaque	Toothpaste Tablet	20	2.59±0.49	0.08	0.579	-0.25	0.417
	Conventional Dentifrice	20	2.56±0.48				

Table 4. Summary of Within Group Analysis of Loe-Silness Gingival Index and Quigley-Hein Plaque Index Scores

						95% Confidence Interval	
Parameter	Dentifrice	N	Mean Difference	Percent Reduction	p-value	Lower	Upper

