Gingivitis	Toothpaste Tablet	20	-0.026	1.9	0.765	-0.117	0.064
	Conventional Dentifrice	20	-0.011	0.8	0.936	-0.070	0.048
Plaque	Toothpaste Tablet	20	-0.224	8.0	0.017	-0.453	0.005
	Conventional Dentifrice	20	-0.218	7.8	0.035	-0.391	-0.045

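### Results Tables 2 to 4 do not reconcile: all four between-group differences miss the printed means, and the tablet plaque change pairs p = 0.017 with a 95% CI that includes zero

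*Combined protocol and SAP*

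**What the plan says.** Section 6a gives the primary endpoint as "GI and PI scores between the use of dental tablets and conventional toothpaste". For the analysis, Section 17 states that "we will use an independent sample t-test to compare the difference in GI and PI scores between the two groups", two-sided at 0.05, with a Mann-Whitney test if scores are not normally distributed. It describes no within-group test and no covariate adjustment.

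The Results tables follow the schedule of events. Tables 2 and 3 give group means and SDs at baseline and two weeks, each pair with a column headed Mean Difference, a p-value and a 95% CI. The baseline GI row for tablets is "Gingivitis Toothpaste Tablet 20 1.35±0.26 -0.08 0.47 -0.19 0.13". At two weeks the GI row for tablets is "Gingivitis Toothpaste Tablet 20 1.33±0.26 -0.06 0.37 -0.167 0.083", against "Conventional Dentifrice 20 1.34±0.18" in the other arm, and the plaque row for tablets is "Plaque Toothpaste Tablet 20 2.59±0.49 0.08 0.579 -0.25 0.417".

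Table 4 gives within-arm changes. The tablet plaque row is "Plaque Toothpaste Tablet 20 -0.224 8.0 0.017 -0.453 0.005" and the conventional GI row is "Conventional Dentifrice 20 -0.011 0.8 0.936 -0.070 0.048". No table in the text names the test behind its p-values or intervals.

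**The concern.** A column of mean differences should equal one printed mean minus the other, apart from rounding. A p-value and a 95% CI from the same test should fall on the same side of 0.05. Neither holds here.

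The two-week rows of Table 3 are the study's main result. Section 12 intends a finding of no difference to encourage people to change product, so the size of the estimate and the limits of the interval carry the message more than a p-value above 0.05 does. In Table 4, whether plaque fell significantly in the tablet arm depends on which of two printed figures the reader believes.

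**Working it through.** **1. Between-group rows (Tables 2 and 3).** Inputs are the printed means and SDs, n = 20 per arm. Difference d = tablet mean - conventional mean; SE = √((s₁² + s₂²)/20); 95% CI = d ± 2.024 × SE (t on 38 df). For two-week GI: d = 1.33 - 1.34 = -0.01; SE = √((0.26² + 0.18²)/20) = 0.0707; half-width 0.143; t = -0.14; p = 0.89.

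| Row | Means | Printed difference | d | Gap | Printed CI (midpoint) | Recomputed CI | Printed p | Recomputed p |
|---|---|---|---|---|---|---|---|---|
| Baseline GI | 1.35, 1.37 | -0.08 | -0.02 | 0.06 | -0.19 to 0.13 (-0.03) | -0.180 to 0.140 | 0.47 | 0.80 |
| Baseline PI | 2.80, 2.78 | 0.06 | 0.02 | 0.04 | -0.36 to 0.38 (0.01) | -0.315 to 0.355 | 0.665 | 0.90 |
| Two-week GI | 1.33, 1.34 | -0.06 | -0.01 | 0.05 | -0.167 to 0.083 (-0.042) | -0.153 to 0.133 | 0.37 | 0.89 |
| Two-week PI | 2.59, 2.56 | 0.08 | 0.03 | 0.05 | -0.25 to 0.417 (0.0835) | -0.280 to 0.340 | 0.579 | 0.85 |

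Rounding each mean (±0.005) and the printed difference (±0.005) allows a gap of at most 0.015; all four exceed it. Subtracting the other way round fits worse.

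Only the two-week PI interval is centred on its printed difference. In the baseline GI row, -0.08 lies 0.11 above the lower limit and 0.21 below the upper. That interval has the half-width the SDs imply (0.160) and is centred near the difference of the means, so it fits the means but not the printed difference.

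Rounding in the means and SDs moves the recomputed two-week p-values only within 0.77 to 1.00 (GI) and 0.79 to 0.90 (PI). The upper limits, where tablets are worse, stay within 0.120 to 0.146 for GI (printed 0.083) and 0.327 to 0.354 for PI (printed 0.417).

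**2. Within-arm p-values against their intervals (Table 4).** SE = half-width/2.093 (t on 19 df), t = change/SE. Every interval is centred on its estimate to within 0.0005, as a t interval would be. For tablet plaque: half-width (0.005 + 0.453)/2 = 0.229; SE = 0.1094; t = -2.05; p = 0.055 (0.0537 to 0.0557 allowing for rounding).

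| Row | Change | Printed CI | SE | t | p implied by CI | Printed p |
|---|---|---|---|---|---|---|
| GI, tablet | -0.026 | -0.117 to 0.064 | 0.0432 | -0.60 | 0.555 | 0.765 |
| GI, conventional | -0.011 | -0.070 to 0.048 | 0.0282 | -0.39 | 0.70 | 0.936 |
| Plaque, tablet | -0.224 | -0.453 to 0.005 | 0.1094 | -2.05 | 0.055 | 0.017 |
| Plaque, conventional | -0.218 | -0.391 to -0.045 | 0.0827 | -2.64 | 0.016 | 0.035 |

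Conversely, p = 0.017 from a paired t-test would go with an interval of about -0.403 to -0.045. A one-sided reading gives 0.027, which does not match either.

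**3. Table 4 changes against Tables 2 and 3.** Conventional GI: 1.34 - 1.37 = -0.03, rounding range -0.04 to -0.02; printed -0.011. As a percentage, 0.03/1.37 = 2.2% against 0.8% printed. This reverses a direction. Table 4 has GI falling 0.015 more with tablets (-0.026 against -0.011), whereas the means have it falling 0.01 less (-0.02 against -0.03). The rounding range for that difference in changes is -0.01 to +0.03, and -0.015 lies outside it. Tablet plaque: 2.59 - 2.80 = -0.21, range -0.22 to -0.20; printed -0.224, a trivial gap of about 0.004.

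The printed percent reductions (1.9, 0.8, 8.0, 7.8) do reproduce from the Table 4 changes over the Table 2 baseline means, so damage to the rows in text extraction is an unlikely explanation.

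**The case against.** The best defence is mixed methods. Section 17 allows a rank test for non-normal scores, so Table 4 could show signed-rank p-values beside t-based intervals. I simulated 20 paired changes scaled to the printed tablet plaque estimate and interval. Signed-rank p-values were at or below 0.02 in about 21% of heavy-tailed samples (t with 3 df), though in under 2% of normal ones. So p = 0.017 beside that interval is possible and is not proof of an arithmetic error. That part stands.

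Tables 2 and 3 could likewise hold differences in medians. With samples fixed to the printed means and SDs, median differences at least as far off as printed, in the same direction, arose in roughly 18% to 42% of samples per row. But the column is headed Mean Difference, so it would then be mislabelled. Baseline adjustment cannot explain Table 2, which is the baseline, and different subjects are not suggested when every row shows N = 20. None of these explanations accounts for the conventional GI change.

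Two further points are fair. If Mann-Whitney was used, the recomputed t-test p-values are not corrections of the printed ones. And the practical effect is limited: no equivalence margin is set, so neither upper limit crosses a threshold, and for PI the printed limit is the more cautious of the two. A footnote naming the test could also have been lost in extraction, although the only visible footnote markers are on product names in Table 1.

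**Conclusion.** The concern holds. All four between-group differences miss the printed means by 0.04 to 0.06, both two-week primary comparisons by 0.05, and the conventional GI change cannot be obtained from Tables 2 and 3. The tablet plaque p-value and interval give opposite answers at 0.05 (0.017 against an implied 0.055) and stay unexplained.

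No between-group inference changes: printed p-values run from 0.37 to 0.665, recomputed ones from 0.80 to 0.90, and every interval includes zero. What changes is the size of the estimate and the excess that is not excluded. For two-week GI the upper limit is about 0.133 rather than 0.083, so the printed limit understates how much worse tablets might be; for PI it is about 0.34 rather than 0.417. The only result to cross 0.05 is a within-arm comparison that Section 17 did not plan.

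The recomputed values assume t methods, n = 20 per arm and correctly printed means and SDs. The documents do not show which column is at fault.

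**What to change.** - Recompute Tables 2 to 4 from the data sheets.
- In each row take the estimate, interval and p-value from one method, name it in a footnote, and label the estimate for what it is: a difference in means, or a rank-based shift.
- Name the paired test used in Table 4 and mark that table as not planned in Section 17.
- Check the conventional GI change, and the small tablet plaque gap, against the means in Tables 2 and 3.
- Until the tablet plaque p-value and interval agree, describe that change as neither significant nor non-significant.

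The cost is a short re-analysis of existing data on 40 subjects and corrected tables. The only downside is that one unplanned within-arm result may lose significance.
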